## **Financial support:**

Self-sponsored

Principal investigator: [name]

## Time periods:

See attached Gwent chart

## **Expected outcome:**

Foam sclerotherapy of the ulcer veins is expected to increase the number of healed ulcers, reduce the time to achieve complete healing, and reduce recurrence rate

#### Safety

Any adverse events should be recorded and reported to the PI

#### Statistical and health economic analysis:

A comprehensive statistical analysis plan will be produced by the study statistician Kaplan-Mayer curves will be created for both Group A and Group B, and will be compared for significance

The total number of patients who achieved complete healing in both groups will be compared Analysis of variance or logistic regression analysis could be used to assess the effect of each variable on healing (age, gender, DM, BMI, ulcer size, and method of treatment)

A health economist will support a health economic evaluation of the study results

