#### **Exclusion criteria:**

- Pregnant and lactating females
- Age <18 years
- Peripheral arterial disease confirmed by ABPI <0.8, or a duplex scan showing significant peripheral arterial disease
- Do not show evidence of a refluxing network of veins in the vicinity of the ulcer; "ulcer veins"
- VLU >2 years duration
- VLU size >20cm in any dimension
- Participant unable to give informed consent

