### Sample size calculations:

Sample sizes were calculated at 90% power with alpha of 5%

The sample standard deviation of healing time in days was 26, with the 'worst case' recorded standard deviation being 39.4

The weighted average of healing time for compression only was 75.4 (based on N=1787)

The weighted average of healing time for compression + intervention was 47.3 (based on N=758)

This represents a large effect size of treatment and, even with the 'worst case' SD, would require a sample size of 42 - I feel this is optimistic, likely overestimates the effect size of the intervention and would result in an underpowered study

If, like EVRA, a 15% effect size was considered this would make the healing time estimate for compression + intervention 64.1 days, giving a sample size of 255 (using the 'worst case' recorded standard deviation of 39.4)

Allowing for a dropout rate of 10% and protocol violations the target sample size can be 300 set at patients

With the more lenient SD of 26, and the EVRA effect size of 15%, the sample size is 112

Allowing for a dropout rate of 10% and protocol violations the target sample size can be 130 set at patients

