#### **Documentation:**

- A secure cloud based digital platform will be created
- Upon randomization, the following data will be collected for each participant:
  - o Unique participant number
  - o **Initial visit clinical assessment:** date, age, gender, clinical center, ulcer size in 2 dimensions, ulcer size as measured by Lesionmeter software, ulcer depth (subjective), ulcer location, ulcer side (right or left lower limb), ulcer duration, presence of pedal pulses, ABPI, history of DVT(s), history of venous intervention(s), type of venous intervention (surgery, ablation, foam, stent), date(s) of venous intervention(s), history of diabetes, HbA1C, BMI (weight and height), cardiac failure (including ejection fraction and NYHA classification), other co-morbidities
  - o **Dressings and compression:** type of ulcer dressing and type of compression used; both recorded at each visit
  - Duplex ultrasound findings: details of superficial and deep system reflux and obstruction
  - o **Foam sclerotherapy:** drug used, concentration, gas used, number of injections, foam volumes injected, number of foam sclerotherapy sessions, perforator treatment
  - Follow up visits: date, ulcer healed?, ulcer size in 2 dimensions, ulcer size as measured by Lesionmeter software, ulcer depth (subjective), foam side effects/complications
  - o **Final visit:** ulcer healed?, ulcer size in 2 dimensions, ulcer size as measured by Lesionmeter software, ulcer depth (subjective), foam side effects/complications
  - **Telephone follow up:** date of date, date of recurrence if any, compliance with compression hosiery
  - o **Ulcer photography:** at least one ulcer photograph at the first visit, and one ulcer or ulcer site photograph during the last visit

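### The only comparison stated for time to healing uses no covariate, although baseline ulcer size is recorded for every participant; a prespecified size-adjusted time-to-event comparison would add power at no data cost, by an amount that has to be assumed

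*Protocol*

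**What the plan says.** Under Objectives, the Protocol makes time to complete healing the single primary objective. Under Statistical and health economic analysis, the only comparison that addresses time is this: "Kaplan-Mayer curves will be created for both Group A and Group B, and will be compared for significance". No test, covariate or stratification factor is named with it.

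The same section adds a comparison of the numbers healed. It then mentions ANOVA or logistic regression as something that may be used to "assess the effect of each variable on healing (age, gender, DM, BMI, ulcer size, and method of treatment"). It also says that a full SAP will be written later by the trial's statistician; that document is not at hand.

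Under Documentation, the initial visit records "ulcer size in 2 dimensions, ulcer size as measured by Lesionmeter software" for each participant. Under Exclusion criteria, the only limit on size is "VLU size >20cm in any dimension", so a wide spread of starting sizes can enter. The Methods section says that patients are randomized to two groups and states no balancing on ulcer size.

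**The concern.** The Protocol names ulcer size as a possible determinant of healing and measures it at entry in two ways, but leaves it out of the one stated comparison of time to healing. The optional model does contain both size and treatment. But logistic regression handles healed yes or no, ordinary ANOVA does not handle censored healing times, and neither is tied to the primary objective.

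If size is prognostic, two things follow. The variation in healing time that it explains stays in the comparison as noise. In a proportional-hazards analysis, omitting a strong prognostic factor also pulls the hazard ratio towards 1. The planned difference is 75.4 − 64.1 = 11.3 days against an SD of 26 to 39.4 days, so the loss could be noticeable. At stake is power and precision, not validity: under randomization the unadjusted test keeps its error rate.

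**Working it through.** **Inputs (Protocol, Sample size calculations).**

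- Significance level 5%, target power 90%.
- Mean under compression alone: 75.4 days, pooled over 1787 patients.
- Intervention mean at the 15% effect: "healing time estimate for compression + intervention 64.1 days, giving a sample size of 255".
- Spread, in the Protocol's words: "The sample standard deviation of healing time in days was 26, with the 'worst case' recorded standard deviation being 39.4".
- Targets after 10% dropout: 300 (SD 39.4) and 130 (SD 26).
- Assumed here because not stated: a two-sided test and 1:1 allocation.

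**Step 1. Reproduce the Protocol's figures.** n per arm = 2 × (1.960 + 1.282)² × SD² / d².

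- SD 39.4, d = 11.3: 21.02 × 1552.36 / 127.69 = 255.5, so 256 (stated 255).
- SD 26, d = 11.3: 21.02 × 676 / 127.69 = 111.3, so 112 (stated 112).
- SD 39.4, d = 75.4 − 47.3 = 28.1: 21.02 × 1552.36 / 789.61 = 41.3, so 42 (stated 42).

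The stated numbers reproduce only as per-arm sizes. As totals they would be 512, 224 and 84 (two-sided) or 418, 182 and 68 (one-sided). Yet the targets look like totals built on those same numbers: 255 / 0.9 = 283.3, so 284, rounded to 300; and 112 / 0.9 = 124.4, so 125, rounded to 130. Both readings are therefore carried forward.

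**Step 2. Power with and without adjustment.** Let R² be the share of variance in healing time explained by baseline size. The Protocol gives no value; 0.05 to 0.30 is an assumption.

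Power = Φ( d / [SD × √(1 − R²) × √(2/n)] − 1.96 ), with n per arm.

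Example, 300 in total (n = 150, SD 39.4): the standard error is 39.4 × √(2/150) = 4.55 and 11.3 / 4.55 = 2.484, so power is Φ(0.524) = 70.0%. At R² = 0.30, 2.484 / √0.70 = 2.969, so power is Φ(1.009) = 84.3%.

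| Reading | Unadjusted | R² 0.05 | R² 0.10 | R² 0.20 | R² 0.30 | Gain (points) |
|---|---|---|---|---|---|---|
| 300 total, SD 39.4 | 70.0% | 72.2% | 74.5% | 79.3% | 84.3% | 2.2 to 14.4 |
| 270 analysed (300 less 10%), SD 39.4 | 65.4% | 67.6% | 70.0% | 75.0% | 80.4% | 2.2 to 15.0 |
| 130 total, SD 26 | 69.8% | 72.0% | 74.3% | 79.1% | 84.2% | 2.2 to 14.4 |
| 117 analysed (130 less 10%), SD 26 | 65.2% | 67.4% | 69.8% | 74.8% | 80.2% | 2.2 to 15.0 |
| 255 per arm, SD 39.4 | 89.9% | 91.3% | 92.7% | 95.2% | 97.2% | 1.4 to 7.3 |
| 112 per arm, SD 26 | 90.2% | 91.6% | 92.9% | 95.3% | 97.3% | 1.4 to 7.1 |

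If 300 is a total but the SD is really 26, power is already 96.4% and the gain is only 0.7 to 3.0 points.

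**Step 3. Cross-check with time-to-event models.** The formula in Step 2 belongs to a linear model, so two simulations compared Cox models with and without the covariate (1,500 runs each, censoring at 365 days).

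- Log-normal times, 270 patients in total: 67.7% unadjusted against 66.9% adjusted at correlation 0 (a difference within simulation error); 68.9% against 72.8% at 0.3 (R² 0.09); 66.7% against 81.3% at 0.5 (R² 0.25).
- Weibull-type times, R² 0.10 to 0.30: gains of 4.7 to 13.1 points at 150 per arm, 6.4 to 18.1 at 135 per arm, and 0.7 to 2.1 at 255 per arm, where unadjusted power is already about 98% to 99%.

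The absolute power depends heavily on the assumed distribution. The direction and rough order of the gain do not.

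**The case against.** The strongest reply is that covariates for the primary model are normal SAP content, and the section promises a SAP. The Protocol never calls the comparison unadjusted, names no test and labels no test as primary. Comparing curves for significance does not exclude a stratified test. The optional regression also shows that ulcer size has been thought of. This stands in part: a reader might infer that the trial has decided against adjustment, and the document does not support that. The loss arises only if the SAP keeps a comparison without covariates. The point survives because the text does state a method for time to healing and puts ulcer size in a different, non-survival model. A SAP that simply follows it would not adjust, and adjustment added after the data are seen would look selective.

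Three other stronger readings are tempting and should be resisted.

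- A reader might infer a definite loss of, say, 4 to 15 points. That range needs R² of about 0.1 to 0.3 and the targets read as two-arm totals. The Protocol gives no correlation, and its sample sizes reproduce only per arm, where the gain is smaller.
- A reader might treat ulcer size as the baseline value of the outcome. The outcome is a time; size at entry is a prognostic covariate, and how strong it is here is unknown.
- A reader might say that chance imbalance in size biases the unadjusted result. It does not: the test's error rate already covers it. Adjustment improves precision and removes the effect of imbalance on the particular estimate.

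It is also fair that Cox against stratified log-rank, and software area against two dimensions, are choices among reasonable options.

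**Conclusion.** The point holds as a recommended improvement to a stated method, not as an error that invalidates the trial. For its primary objective the Protocol states only a two-group comparison of Kaplan-Meier curves, while a likely prognostic variable measured in everyone is confined to an optional analysis that is not time-to-event.

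By the formula, the benefit of adjusting is about 2 to 15 points of power for R² 0.05 to 0.30 if 300 (or 130) is a two-arm total, about 1 to 7 points if 255 is per arm, and nil if size is not prognostic, with almost no loss in that case. These figures rest on an assumed R², 1:1 allocation, a two-sided 5% test and a linear-model approximation that the simulations support in direction. Confidence is medium because the SAP is not shown.

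Adjustment should not be taken as a remedy for the sample size. If the targets are totals, unadjusted power is about 65% to 70%, and even R² = 0.30 brings it only to about 80% to 84%, short of the stated 90%. The per-arm or total question has to be settled separately.

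**What to change.** In the Statistical and health economic analysis section, and then in the SAP, state before any outcome data are examined that the primary comparison is the Group A to Group B hazard ratio for time to complete healing from a Cox model adjusted for baseline ulcer size as recorded at entry, for example the log of the Lesionmeter area. A log-rank test stratified by baseline size is an acceptable alternative. Fix the chosen size measure in advance. Keep the Kaplan-Meier curves as the display and the unadjusted log-rank test as a supporting analysis.

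The cost is one sentence, with no new measurements or patients. The small downside is that the adjusted hazard ratio is conditional on ulcer size, so the unadjusted result should be reported beside it. If a power gain is quoted, show it over a range of assumed R².

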### **Publication:**

Publication of the study protocol and results expected in high impact factor journals Authorship: all investigators are expected to be co-authors, however the international rules for authorship will be observed

## **Expected problems:**

Recruitment: patients meeting inclusion/exclusion criteria; patients refuse to consent to randomization

Loss to follow-up

Operators deviate from protocol

Patient non-compliance with compression

